### **2.2. Final Analysis**

After all subjects have completed/discontinued the study, outstanding data queries have been resolved or adjudicated as unresolvable, and the data have been cleaned and finalized, the final analysis of the data will be performed.

### **2.3. Follow-up Analysis**

No follow-up analysis is planned for this study.

### **3. GENERAL CONSIDERATIONS FOR DATA ANALYSES**

Analysis results will be presented using descriptive statistics. For categorical variables, the number and percentage of subjects in each category will be presented; for continuous variables, the number of subjects (n), mean, standard deviation (StD) or standard error (SE), median, first quartile (Q1), third quartile (Q3), minimum, and maximum will be presented.

By-subject listings will be presented for all subjects in the All Enrolled Analysis Set and sorted by subject ID number, visit date, and time (if applicable). Data collected on log forms, such as AEs, will be presented in chronological order within the subject. The treatment group to which subjects were initially assigned will be used in the listings. Age, sex at birth, race, and ethnicity will be included in the listings, as space permits.

#### **3.1. Analysis Sets**

Analysis sets define the subjects to be included in an analysis. Analysis sets and their definitions are provided in this section. The analysis set will be identified and included as a subtitle of each table, figure, and listing.

For each analysis set, the number and percentage of subjects eligible for inclusion will be summarized by cohort and overall.

A listing of reasons for exclusion from analysis sets will be provided by subject.

##### **3.1.1. All Enrolled Analysis Set**

All Enrolled Analysis Set includes all subjects who received a study subject identification number in the study after screening.

##### **3.1.2. Safety Analysis Set**

The Safety Analysis Set includes all subjects who took at least 1 dose of study drug. This is the primary analysis set for safety analyses.

##### **3.1.3. Dose-Limiting Toxicity (DLT) Analysis Set**

DLTs will only be evaluated for subjects in Cohort 1. The DLT Analysis Set includes Cohort 1 subjects in the Safety Analysis Set who complete all study treatment and have safety assessments through the protocol specified DLT assessment window, Day 28, inclusive, or have experienced a DLT prior to Day 28, exclusive. This is the primary analysis set for analyses related to DLTs in Cohort 1. Safety assessments relevant to the DLT analysis set definition will include serum chemistry, hematology and coagulation tests as specified in the protocol.

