5.3.1.1. Andecaliximab

In Cohort 1 (andecaliximab monotherapy), if a subject experiences a DLT (see Section 3.2 for the definition of a DLT), andecaliximab treatment will be postponed until the toxicity is resolved to Grade 0 or 1 (as defined by the Common Terminology Criteria for Adverse Events (CTCAE), version 4.03 or returns to the subject's baseline value. If the toxicity is resolved to Grade 0 or 1, or returns to the subject's baseline value within 28 days from the start of the event, the subject may resume andecaliximab at 50% of the originally assigned dose level. If the subject experiences a recurrence of the toxicity meeting criteria for DLT after restarting andecaliximab

or if the toxicity does not resolve within 28 days, treatment with andecaliximab will be discontinued. Alternatively, if there is no recurrence of the toxicity, the dose of andecaliximab may be increased to 100% of the originally assigned level after discussion with the medical monitor.

Dose modification or delay of andecaliximab following adverse events that do not meet the criteria for a DLT (either during the DLT window or afterwards for subjects in Cohort 1) may be permitted at the discretion of the Investigator after discussion with the medical monitor.

For subjects enrolled in the combination therapy cohorts (Cohorts 2-4), dose delay of andecaliximab following adverse events may be permitted at the discretion of the Investigator after discussion with the medical monitor. Dose modification of andecaliximab is not permitted in the combination therapy cohorts without prior discussion with the medical monitor.

Additionally, in the combination therapy cohorts, subjects in whom anti-cancer agent (SP, SOX, or nivolumab) administration must be delayed may continue to receive andecaliximab while anti-cancer agent(s) are held, in the absence of disease progression. If anti-cancer agent treatment (SP, SOX, or nivolumab) is permanently discontinued, andecaliximab treatment must be permanently discontinued. Subjects enrolled in Cohorts 2 and 3 may permanently discontinue 1 of the 2 anti-cancer agents (ie, cisplatin or oxaliplatin) for reasons other than disease progression, and still continue treatment with S-1 and andecaliximab until they meet 1 of the discontinuation criteria in Protocol Section 3.5 or 3.7.

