Subjects who discontinue andecaliximab for reasons other than disease progression may continue to receive anti-cancer agent treatment (SP, SOX, or nivolumab) until disease progression.

If the subject was not receiving andecaliximab at the time disease progression was documented (eg, due to reversible toxicity), after discussion with the medical monitor, andecaliximab may be re-started if the criteria for resuming treatment as described in Section 5.3.1.1 are met and the investigator feels it is in the subject's best interest to do so.

Dose delay of andecaliximab due to holidays, site closures and subject availability may be permitted after discussion with the medical monitor. The reason for interruption or delay should be documented in the subject's study record.

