6. STUDY PROCEDURES

The study procedures to be conducted for each subject enrolled in the study are presented in tabular form in [Appendix 2-Appendix 5](#) and described in the text that follows.

The investigator must document any deviation from protocol procedures and notify the sponsor or contract research organization (CRO).

Safety and tolerability assessments will include regular monitoring of AEs, changes from baseline in laboratory variables, PEs, vital signs, and special safety assessments like ECGs.

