6.3.4. Day 15 of Each 28-Day Cycle

The following will be performed and documented on Day 15 (\pm 1 day):

Pre Dose:

- Modified PE capturing changes from prior examinations and weight
- Vital signs including blood pressure, respiratory rate, pulse, and temperature
- ECOG Performance Status
- Obtain blood and/or urine samples for:
 - Chemistry (See Section 6.12.8)

- Hematology (See Section 6.12.8)
- Coagulation (See Section 6.12.8)
- Andecaliximab concentration (Day 15 of Cycle 1 only) (See Section 6.12.8)
- Blood biomarkers (See Section 3.11)
- Obtain tumor tissue biopsy (Day 15 of Cycle 2 (+5d) only) and perform endoscopic evaluation noting extent and grade of disease and new instances of, or progression of, existing gastritis and dysplasia before biopsies
- Urinalysis (See Section 6.12.8)
- Review of concomitant medication(s)
- Record any SAEs and all AEs related to protocol mandated procedures

Dosing:

- Administer andecaliximab via IV infusion over approximately 30 (\pm 5) minutes

Post Dose: End of Infusion (EOI)

- Obtain blood samples for:
 - Andecaliximab concentration (30 ± 15 minutes, Day 15 of Cycle 1 only) (See Section 6.12.8)
- Record any SAEs and all AEs related to protocol mandated procedures

6.3.5. Cycle 1 Day 29/Cycle 2 Day 1

The Cycle 1 Day 29 visit, which overlaps with the Cycle 2 Day 1 visit, is the end of the DLT assessment window. In order for a subject to be evaluable for the DLT observation, the subject must have received the first dose of andecaliximab, completed all safety procedures through Day 28, or have experienced a DLT prior to Day 28. Assessments should be performed as listed in Section 6.3.1 for Day 1 of each 28-day cycle. Additionally, see Section 6.5 for Continuation of Treatment Assessments.

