- l EOT assessments will be requested by subjects who discontinue all treatment prior to disease progression. These assessments should be completed as soon as possible after the decision is made. Every attempt should be made to keep the subject in the study and continue to perform tumor evaluation by CT or MRI every 8 weeks until disease progression. Blood samples for hematology, coagulation, chemistry, blood biomarkers, andecaliximab concentration and anti-andecaliximab antibodies should only be collected if not conducted in the last 2 weeks.
- m A safety follow-up visit will be performed 30 days (± 7 days) after the last dose of andecaliximab. The 30-day safety follow-up visit may be substituted by a scheduled study visit if it occurs within the same window.
- n Blood samples for biomarkers will be collected Pre Dose on Day 1 of each cycle, Day 15 of Cycles 1 and 2, and every 8 weeks, at the EOT (if not conducted in the last 2 weeks) visit, and EOS visit. Additionally, blood samples for biomarkers will be collected on Days 2, 4, and 8 of Cycle 1.
- o Tumor tissue biopsy must be collected within 28 days prior to first dose and on Cycle 2 Day 15 (+ 5 days). Endoscopic samples (minimum 4, but 6-8 encouraged) to be processed as described in the laboratory manual.
- p Normal gastric tissue biopsy must be collected within 28 days prior to first dose (Day 1 of Cycle 1 Pre Dose). Endoscopic samples (minimum 4, but 6-8 encouraged) to be processed as described in the laboratory manual.
- q The Cycle 1 Day 29 visit, which overlaps with the Cycle 2 Day 1 visit, is the end of the DLT assessment window. In order for a subject to be evaluable for the DLT observation, the subject must have received the first dose of GS-5745, completed all safety procedures through Day 28, or have experienced a DLT prior to Day 28. Assessments should follow schedule for Day 1 of each 28-day cycle.
- r LTFU for OS begins after the EOS visit or the last visit on study if EOS does not occur. Subjects will be contacted via phone call every 3 months for determination of long term survival status and record of any other anti-cancer therapy, cancer-related surgery for up to 5 years after the EOS visit.

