  - k. Every 8 Weeks ( $\pm 5$  days) assessments will be performed for subjects continuing treatment, or subjects who discontinue all treatment prior to disease progression but remain on study. If a subject *discontinues study drug (for example, as a result of an AE)*, every attempt should be made to keep the subject in the study to collect tumor assessments (CT/MRI), and blood samples for chemistry, hematology, coagulation, and blood biomarkers (if not collected in the last 2 weeks) every 8 weeks until disease progression.
  - l. EOT assessments will be requested by subjects who discontinue all treatment prior to disease progression. These assessments should be completed as soon as possible after the decision is made. Every attempt should be made to keep the subject in the study and continue to perform tumor evaluation by CT or MRI every 8 weeks until disease progression. Blood samples for hematology, coagulation, chemistry, blood biomarkers, andecaliximab concentration and anti andecaliximab antibodies should only be collected if not conducted in the last 2 weeks.
  - m. A safety follow up visit will be performed 30 days ( $\pm 7$  days) after the last dose of andecaliximab. The 30 day safety follow up visit may be substituted by a scheduled study visit if it occurs within the same window.
  - n. Blood samples for biomarkers will be collected Pre Dose on Day 1 of each cycle, Day 15 of Cycles 1 and 2, and every 8 weeks, at the EOT (if not conducted in the last 2 weeks) visit, and EOS visit. Additionally, blood samples for biomarkers will be collected on Days 2, 4, and 8 of Cycle 1.
  - o. Tumor tissue biopsy must be collected within 28 days prior to first dose and on Cycle 2 Day 15 (+ 5 days). Endoscopic samples (minimum 4, but 6-8 encouraged) to be processed as described in the laboratory manual.
  - p. Normal gastric tissue biopsy must be collected within 28 days prior to first dose (Day 1 of Cycle 1 Pre Dose). Endoscopic samples (minimum 4, but 6-8 encouraged) to be processed as described in the laboratory manual.
  - q. The Cycle 1 Day 29 visit, which overlaps with the Cycle 2 Day 1 visit, is the end of the DLT assessment window. In order for a subject to be evaluable for the DLT observation, the subject must have received the first dose of GS 5745, completed all safety procedures through Day 28, or have experienced a DLT prior to Day 28. Assessments should follow schedule for Day 1 of each 28 day cycle.

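### SAP section 3.1.3 makes completion of all study treatment a condition of the Cohort 1 DLT Analysis Set; the protocol's DLT-evaluability rule asks only for the first dose

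*SAP*

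**What the plan says.** SAP section 3.1.3 sets up the primary analysis set for Cohort 1 DLTs. Apart from subjects with a DLT before Day 28, it takes those in the "Safety Analysis Set who complete all study treatment and have safety assessments through the protocol specified DLT assessment window", up to and including Day 28. Its last sentence adds: "Safety assessments relevant to the DLT analysis set definition will include serum chemistry, hematology and coagulation tests".

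Protocol section 6.3.5 states who is evaluable for DLTs. To be counted, each participant "must have received the first dose of andecaliximab, completed all safety procedures through Day 28, or have experienced a DLT prior to Day 28". Footnote q of protocol Appendix 2 repeats this ("the subject must have received the first dose of GS-5745, completed all safety procedures through Day 28"), and SAP Appendix 1 reproduces the footnote ("the subject must have received the first dose of GS 5745, completed all safety procedures through Day 28").

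Protocol section 5.3.1.1 allows dosing to be delayed or modified, after discussion with the medical monitor, "following adverse events that do not meet the criteria for a DLT (either during the DLT window or afterwards for subjects in Cohort 1"). It also provides that "Dose delay of andecaliximab due to holidays, site closures and subject availability may be permitted". Protocol section 6.11 replaces a Cohort 1 subject only on withdrawal from the study before the window closes for a reason other than a DLT.

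SAP section 7.1.7.1 summarizes DLTs on the section 3.1.3 set. SAP section 7.7, which lists changes from the protocol's safety analyses, mentions only that continuous safety data will not be summarized.

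**The concern.** The SAP has two evaluability rules for the same six-subject cohort, one in section 3.1.3 and one in its Appendix 1, and only the second agrees with the protocol. The section 3.1.3 rule is the one that will be programmed. It turns a permitted dosing delay into a reason for exclusion, even when the subject was watched for the whole window and had no DLT.

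Safety and tolerability is the primary objective, and the DLT rate is the most compact summary of it for the monotherapy dose. If the set is smaller than the group the safety review team (SRT) called DLT-evaluable, the CSR will show a denominator that differs from the one behind the dose decision. Nothing in section 7.7 would tell the reader why.

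**Working it through.** **The plan's own figures.** SAP section 1.2 gives 6 DLT-evaluable subjects, reviewed on 11 May 2017. SAP section 1.3 states a probability above 65% of seeing 2 or more DLTs among 6 when the true rate exceeds 33.3%. At a rate of exactly 1/3:

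1 − (2/3)^6 − 6 × (1/3) × (2/3)^5 = 1 − 0.0878 − 0.2634 = 0.649.

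This agrees with the stated figure to rounding, so N = 6 is the intended denominator.

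**The two rules side by side, for a subject without a DLT.**

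| Condition | Protocol 6.3.5 and footnote q | SAP 3.1.3 |
|---|---|---|
| Dosing | First dose received | All study treatment completed through Day 28 |
| Safety follow-up | All safety procedures through Day 28 | Safety assessments through Day 28, three laboratory panels named |

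The alternative route, a DLT before Day 28, is the same in both.

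**Where they part.** Cohort 1 has two infusions due in the window, on Day 1 and Day 15. Take a subject who receives Day 1, attends every safety visit through Day 28, has no DLT, and has the Day 15 infusion held until after Day 28.

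- Protocol 6.3.5: first dose received and procedures complete, so evaluable.
- Protocol 6.11: not withdrawn, so not replaced.
- SAP 3.1.3: Day 15 infusion not given by Day 28, so treatment through the window is not complete and the subject is excluded.

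**How narrow the case is.** A late Day 15 infusion given by Day 28 causes no exclusion. A toxicity delay of more than 14 days is itself a DLT criterion. Day 15 + 14 days = Day 29, so for an infusion due exactly on Day 15, a toxicity hold with dosing resumed on Day 29 stays below that threshold. The ±1 day visit window can shift this by a day. Holds for site closure, holiday or subject availability have no such limit.

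**Size.** The combination cohorts were to open only with 0 or 1 DLT in 6. They went ahead at 800 mg every 2 weeks (1200 mg every 3 weeks in Cohort 3), so 0 or 1 DLT is the reasonable inference. If one DLT-free subject is dropped:

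- with 0 DLTs, 0/6 = 0% and 0/5 = 0%, so only N changes;
- with 1 DLT, 1/6 = 16.7% becomes 1/5 = 20.0%, a difference of 3.3 percentage points.

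**The case against.** **All study treatment may mean treatment as the protocol permits it.** On that reading a subject on an approved hold has complied. *Through* might also govern both verbs, so that the phrase means only staying on treatment during the window. Either reading removes the conflict, but section 3.1.3 states neither, and whoever derives the set must choose. The protocol's rule leaves no such choice on dosing.

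**Footnote q is not an independent SAP definition.** This stands. SAP Appendix 1 reproduces the protocol's schedule, so the three places count as one definition repeated. It is still in the SAP and still disagrees with section 3.1.3.

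**The laboratory sentence.** A reader might infer that section 3.1.3 also cuts the required follow-up to three laboratory panels, although the protocol's safety assessments comprise "regular monitoring of AEs, changes from baseline in laboratory variables, PEs, vital signs, and special safety assessments like ECGs". The text does not establish that. It says the relevant assessments *will include* those panels and does not say that they are the only ones. A subject with every in-window laboratory test but no other follow-up is also unlikely. Those tests fall on Days 8 and 15, when AEs and vital signs are also assessed, with a physical examination on Day 15. The sentence deserves clarification and is not a second defect.

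**The practical consequence is very small.** Largely true. SAP section 3.1 promises a by-subject listing of reasons for exclusion, and section 7.1.7.1 lists the DLT events, so a careful reader could rebuild the denominator. That limits the harm, but the primary DLT set would still follow a rule that the protocol does not contain.

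**Conclusion.** The mismatch is real and minor. Section 3.1.3 applies a stricter dosing condition than the protocol's definition of DLT-evaluable, without declaring it, and on its plain reading can remove a fully observed, DLT-free subject from the primary DLT denominator. With one subject removed, the reported rate moves by 3.3 points if there was 1 DLT, and not at all if there were none. The removal of a subject is an assumption; nothing in the documents shows that any Cohort 1 subject had a dose held past Day 28.

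A reader might infer that the dose decision or the design's detection probability is weakened, since the same binomial calculation with 5 subjects gives 0.539 instead of 0.649. The documents do not support that. The SRT decided on 6 DLT-evaluable subjects on 11 May 2017, before the 14 July 2017 protocol amendment on which the SAP is based. The section 3.1.3 set only reports DLTs afterwards.

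**What to change.** In SAP section 3.1.3, replace the treatment-completion condition with the protocol's criterion, so that a Cohort 1 subject in the set "must have received the first dose of andecaliximab, completed all safety procedures through Day 28, or have experienced a DLT prior to Day 28". Reword the last sentence so that chemistry, hematology and coagulation are given as examples of the safety procedures and cannot be taken for the full list.

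If the SAP is already final, record the change in the CSR, as SAP section 1 provides for changes after finalization.

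The cost is two edited SAP sentences, or a short CSR note. No new data, tables or protocol changes are needed.

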3.2. Study Design

This is a Phase 1b, open-label, multicenter study to evaluate the safety and tolerability of andecaliximab as monotherapy and in combination with anti-cancer agents in Japanese subjects with inoperable advanced or recurrent gastric or GEJ adenocarcinoma. The study will comprise 4 cohorts, 1 monotherapy cohort, and 3 combination therapy cohorts.

Cohort 1 is andecaliximab monotherapy. Cohort 2 is combination therapy of andecaliximab with SP. Cohort 3 is combination therapy of andecaliximab with SOX. Cohort 4 is combination therapy of andecaliximab and nivolumab. Up to 38 subjects are expected to be enrolled in the study.

For Cohorts 1, 2, and 4, computed tomography (CT) or magnetic resonance imaging (MRI) scans will be performed every 8 weeks to evaluate response to treatment by RECIST v1.1. For Cohort 4, response to treatment will also be evaluated using immune-related response criteria recommendations {[Wolchok 2009](#)}.

For Cohort 3, CT or MRI scans will be performed every 9 weeks to evaluate response to treatment by RECIST v1.1.

Cohort 1: Andecaliximab Monotherapy

Up to 6 Japanese subjects with inoperable advanced or recurrent gastric or GEJ tumors will be enrolled to receive andecaliximab 800 mg via IV infusion over approximately 30 (\pm 5) minutes Q2W until disease progression.

The DLT assessment window is 28 days. The safety and tolerability of the 800 mg dose will be assessed after all 6 subjects have been followed for at least 28 days after the first infusion of andecaliximab. If 2 or more subjects within the cohort of 6 subjects experience DLTs during the first 28 days of andecaliximab dosing, up to 6 additional subjects will be enrolled at a reduced dose of 600 mg Q2W. If 2 additional DLTs occur at 600 mg, andecaliximab will be considered unsafe and will be discontinued. Therefore, a total of up to 12 subjects may be enrolled in Cohort 1.

A DLT is a toxicity defined below, considered possibly related to andecaliximab occurring during the DLT assessment window (Day 1 through Day 28).

- Grade 4 neutropenia (absolute neutrophil count [ANC] $<$ 500/ μ L) for $>$ 7 days, or febrile neutropenia (per the National Cancer Institute (NCI) Common Terminology Criteria for Adverse Events (CTCAE) Version 4.03 definition) regardless of duration

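### In SAP 3.1.3 a DLT qualifies a subject for the DLT Analysis Set only through Day 27, one day short of the protocol's window, so a Day 28 DLT could be left out of the DLT summary

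*SAP*

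**What the plan says.** SAP 3.1.3 gives a Cohort 1 subject in the Safety Analysis Set two routes into the DLT Analysis Set:

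- Completer route: subjects "who complete all study treatment and have safety assessments through the protocol specified DLT assessment window, Day 28, inclusive".
- DLT route: "or have experienced a DLT prior to Day 28, exclusive".

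It then names the tests that matter for the definition: "Safety assessments relevant to the DLT analysis set definition will include serum chemistry, hematology and coagulation tests as specified in the protocol".

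The protocol draws the boundary elsewhere. Section 3.2 (and the synopsis) defines a DLT as a toxicity "occurring during the DLT assessment window (Day 1 through Day 28", and the dose rule applies "If 2 or more subjects within the cohort of 6 subjects experience DLTs during the first 28 days of andecaliximab dosing". Yet the evaluability sentence in Protocol 6.3.5 requires the first dose and that the subject "completed all safety procedures through Day 28, or have experienced a DLT prior to Day 28". Footnote q of Protocol Appendix 2 repeats that sentence, and SAP Appendix 1 copies it. Section 6.3.5 also states: "The Cycle 1 Day 29 visit, which overlaps with the Cycle 2 Day 1 visit, is the end of the DLT assessment window".

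SAP 7.1.7.1 builds the DLT summary on the DLT Analysis Set. It also promises a DLT listing, with no restriction to that set.

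**The concern.** A set used to tabulate DLTs should contain every subject who had one inside the window. This definition does not guarantee that. The DLT route closes a day before the window does, and the word exclusive removes any reading of the cutoff as including Day 28. SAP 3.8.1 numbers the first-dose day as Day 1, so day counting does not close the gap.

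A subject left out this way would be left out because of the outcome being measured, and would leave both the numerator and the denominator. Protocol 6.11 replaces only subjects withdrawn for reasons other than a DLT, so nobody would fill the place. In a cohort of six, one subject is visible in the table.

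**Working it through.** **The plan's own figure.** SAP 1.3 and Protocol 8.9 state a probability above 65% of seeing 2 or more DLTs in 6 subjects when the true rate exceeds 33.3%. The binomial tail at p = 1/3 is 1 − (2/3)^6 − 6 × (1/3) × (2/3)^5 = 1 − 64/729 − 192/729 = 473/729 = 0.649. It passes 0.65 at p = 0.3339, so the statement holds to rounding. It assumes that every in-window DLT is counted.

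**Day boundaries.**

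| Rule | Days on which a DLT counts |
|---|---|
| DLT definition and dose rule, Protocol 3.2 | 1 to 28 |
| DLT route, SAP 3.1.3 | 1 to 27 |
| DLT clause of the evaluability sentence, Protocol 6.3.5 | before 28 |

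The DLT route covers 27 of 28 days.

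**What the completer route asks of a subject with a Day 28 DLT.**

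1. Treatment. I read completing all study treatment as receiving the Cycle 1 doses due in the window, on Days 1 and 15. Protocol 5.3.1.1 allows andecaliximab to be delayed for adverse events that are not DLTs, so a subject could reach Day 28 without the Day 15 dose. Protocol 6.3.5 asks only for the first dose, so the SAP is stricter here.
2. Tests. In Cohort 1, chemistry and hematology are scheduled on Days 1, 8 and 15 and at the Day 29 visit. Coagulation is scheduled on Days 1 and 15 and at the Day 29 visit. The closing sample therefore belongs to the Day 29 visit. Day 1 pre-dose samples may be drawn up to 2 days early (Protocol 6.12.8; Appendix 2, footnote h), and Day 29 is Cycle 2 Day 1, so the sample can fall as early as Day 29 − 2 = Day 27.

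If both conditions are met, the subject is in the set. If either fails, neither route admits the subject.

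**Effect of one affected subject.** With x DLTs among n subjects, the tabulated rate moves from x/n to (x − 1)/(n − 1), a fall of (n − x)/[n(n − 1)]. This is never negative, and it is zero when x = n. For n = 6 and x = 1, 1/6 (16.7%) becomes 0/5 (0%). The exact 90% interval, the type named in Protocol 8.3, moves from 0.9%–58.2% to 0%–45.1%.

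**How often.** The documents give no DLT timing. Assuming uniform onset over the window, 1/28 = 3.6% of DLTs start on Day 28. That bounds the share affected from above, because the completer route must also fail.

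**The case against.** The strongest reply is that a Day 28 DLT normally stays in. The two clauses can be read as complementary: observed through Day 28, or stopped earlier by a DLT. A subject on study on Day 28 has missed no test due by then. That reading is possible, but it would also accept a subject dosed on Day 15 and lost on Day 16, and Protocol 6.3.5 ties the end of the window to the Day 29 visit. It is not safe to rely on it.

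Other points stand. Under Protocol 5.3.1.1 a DLT leads first to postponed treatment, not withdrawal, so the Day 29 visit will usually take place. Closing tests can also come from an early pre-dose draw, an end-of-study visit (6.9), an unscheduled visit (6.12.12) or repeat testing of Grade 3 or 4 abnormalities (7.6). An end-of-treatment visit (6.8) can supply them too, though only if they were not done in the last 2 weeks, and Day 28 is 13 days after a Day 15 draw. Exclusion needs a further coincidence beyond onset on Day 28.

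A reader might infer three stronger things that the documents do not support:

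- **That two DLTs could be shown as one, 2/6 as 1/5.** Two DLTs would have triggered the 600 mg step. Instead, the safety review of six DLT-evaluable subjects, completed on 11 May 2017, set 800 mg for Cohorts 2 and 4, and SAP 3.2 lists Cohort 1 only at 800 mg.
- **That there is a 6.9% chance of the problem.** The figure 1 − (1 − 1/84)^6 = 6.9%, with 1/84 = (1/3)/28, is the chance of any Day 28 DLT among six subjects, at a DLT rate of one third and uniform onset. It ignores the completer route and is only an upper bound under those assumptions.
- **That the rule always lowers the rate.** It never raises it, but 6/6 would become 5/5.

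**Conclusion.** The mismatch is real and minor. As written, SAP 3.1.3 does not ensure that a subject with a Day 28 DLT is in the set used to summarize DLTs. The subject is lost only if a Cycle 1 dose was missed or the closing tests were not obtained. The 3.6% rests on assumed uniform onset, and the documents give no rate for failure of the completer route.

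The reach is one descriptive table in a study without formal testing (SAP 3.5). A reader might take this as a threat to the dose decision or as a loss of safety data. It is neither. The protocol's rule counts DLTs in the first 28 days without reference to the SAP set. By-subject listings cover all enrolled subjects (SAP 3), and the treatment-emergent adverse event tables use the Safety Analysis Set (SAP 7.1.6).

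Nothing shows that an affected subject exists, and the record of six DLT-evaluable subjects makes one unlikely. It does not rule one out, because the SAP's treatment condition is stricter than the protocol's evaluability sentence.

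**What to change.** In SAP 3.1.3, replace the DLT route with: *or have experienced a DLT on or before Day 28 (Day 1 through Day 28, inclusive)*. Every subject with an in-window DLT is then in the set, whatever treatment or assessments follow, and the case above is tabulated as 1/6.

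The cost is a few words, with no new data and no change to any other analysis. If the SAP is already final, its Introduction allows the change to be documented in the clinical study report.

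The evaluability sentence in Protocol 6.3.5 and Appendix 2 footnote q, copied in SAP Appendix 1, should be reconciled with the Day 1 to Day 28 window at the next amendment. Protocol changes need ethics committee approval (9.2.1), so an amendment for this alone would be out of proportion. The SAP edit is enough to correct the table.
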